9.1.1 Primary Efficacy Endpoint

The primary endpoint is based on the change in mean NRS score assessing average pain intensity in the past 24 hours from baseline to Week 4.

9.1.2 Primary Efficacy Endpoint Analysis

The primary endpoint for mean change from baseline to Week 4 will be summarized with the same ANCOVA model described in Section 5.3.5.2. Additionally, 2 ANCOVA models will be provided for subjects using or not using at least 1 concomitant analysesic medication at Baseline^[4].

9.1.3 Primary Efficacy Endpoint Sensitivity Analyses

Missing values that occurred between Study Day 1 through Day 28 for individual NRS scores assessing average pain intensity in the past 24 hours will be imputed in sensitivity analysis. Any missing data for individual scores not collected at Baseline (Study Day -7 through Day -1) will not be imputed. The following 3 imputation methods will be applied:

- Method 1^[10]: Model-Based using SAS® procedures PROC MI and PROC MIANALYZE
 - o Individual missing scores will imputed 5 times^[11] with a random seed number of 8743216514.
 - The Markov chain Monte Carlo method will be used to compute full imputations using the following variables: planned treatment arm and scores at Study Day 1 through Day 28.

- Method 2^[4]: Last Observation Carried Forward (LOCF)
 - Individual missing scores will use the last individual study day value that was collected and will continue to carry that forward until an observed score was collected
 - If Day 1 is missing, then the mean baseline value will be used (not just the Study Day -1 score).
- Method 3^[4]: Baseline Observation Carried Forward (BOCF)
 - o Individual missing scores will use the mean baseline value calculated.

Once the missing data has been imputed based on one of the following methods, the post-baseline analysis visits will be recalculated if they could not be calculated before. For example, if a subject has observed scores collected for Days 22, 23, 24, and 25 then the observed Week 4 analysis visit mean was already calculated. As a result, imputed Days 26, 27, and 28 will not be used in calculation for the Week 4 analysis visit.

No descriptive statistics tables will be created for any of these imputation methods. The mean change from baseline results in Methods 2 (LOCF) and 3 (BOCF) will be summarized with the same ANCOVA model stated in Section 9.1.2.

The mean change from baseline results in Method 1 (Model-Based) will be summarized into 5 individual ANCOVA models stated in Section 9.1.2 based on the imputation number. From there the ANCOVA statistics will be analyzed in PROC MIANALYZE to produce overall statistics for:

- n =the number of records for that treatment or pooled treatment group
- Least Squares Mean for the treatment groups
- Standard Error for the treatment groups
- Least Squares Mean Difference for the NYX-2925 treatment groups versus Placebo
- Standard Error Difference for the treatment groups versus Placebo
- 95% Confidence Interval for the Difference for the treatment groups versus Placebo
- P-value for the Difference for the treatment groups versus Placebo

Here is the SAS® code for Method 1:

RUN;

```
PROC MI DATA=ADAM NIMPUTE=5 SEED=8743216514 MINIMUM=0 MAXIMUM=10
OUT=ADAM_IMPUTE;
CLASS TRTP;
MCMC INITIAL = EM;
VAR TRTP BASE CHG1 -- CHG28;
RUN;
PROC MEANS;
BY _IMPUTATION_ AVISIT;
VAR CHG;
OUTPUT OUT=ADAM_IMPUTE_MEANS MEAN=CHG;
```

Protocol No.: NYX-2925-2001

```
ODS OUTPUT PARAMETERESTIMATES=MIXPARMS;

PROC MIXED DATA=ADAM_IMPUTE_MEANS ORDER=DATA METHOD=REML;

BY _IMPUTATION_;

CLASS TRTP;

MODEL CHG = BASE TRTP / DDFM=KENWARDROGER;

LSMEANS TRTP / DIFF CL ALPHA=0.05;

/* -1 = Placebo; 0 = 10 mg of NYX-2925; 0.5 = 200 mg and 50 mg of NYX-2925 */

LSMESTIMATE "200 mg and 50 mg of NYX-2925 versus Placebo" TRTP 0 0.5 0.5 -1 / CL;

RUN;

PROC MIANALYZE PARMS=MIXPARMS ALPHA=0.05 MULT;

CLASS TRTP;

MODELEFFECTS INTERCEPT TRTP;

RUN;
```

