4.4 Sample Size Considerations

The planned sample size is 75 randomized subjects per group for a total of 300 randomized subjects.

The mean and standard deviation for reduction in pain from baseline for placebo and active drug were estimated from publicly available sources on duloxetine, pregabalin, gabapentin, and oxycodone. The mean difference from placebo based on higher dose groups (duloxetine \geq 60 mg once daily and pregabalin \geq 300 mg) was estimated at 1.05. The standard deviation was estimated as 2.25.

A sample size of 75 subjects per group will provide approximately 80% power for a 2-sided t-test with Type I error of $0.05^{[5]}$ when the mean difference from placebo is 1.05 and the standard deviation is 2.25.

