5.3.5 Efficacy Data Statistical Inference

5.3.5.1P-values

P-values will be reported out and rounded off to 4 numbers after the decimal point (i.e. "0.####). Any p-values that are > 0.9999 will be reported as ">.9999" in the tables. Any p-values that are < 0.0001 will be reported as "<.0001" in the tables.

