5.6 Multiplicity Adjustments and Type I Error

No formal adjustments for multiplicity will be performed for this phase 2 study. All p-values will be tested using alpha at the 0.05 level, two-tailed.

As an exploratory procedure, multiple comparisons for the primary endpoint may be performed, using Hochberg's procedure^[6]. Only the individual NYX-2925 treatment arms versus Placebo would use this method. The Type I error would be set at 0.05. A nested testing procedure is used after the p-values are ranked from largest to smallest. These are the 3 steps that would be followed:

- Step 1: if the largest observed p-value is \leq 0.05, then statistical significance would be declared for all 3 comparisons.
- Step 2: if the largest observed p-value is > 0.05, then the remaining 2 comparisons would be tested against 0.05 / 2 = 0.025. If the second largest observed p-value is ≤ 0.025 , then statistical significance would be declared for the 2 smallest p-value comparisons.
- Step 3: if the second largest observed p-value is > 0.025, then the last comparison would be tested against 0.05 / 3 = 0.017. If the smallest observed p-value is ≤ 0.017 , then statistical significance would be declared only for the smallest p-value comparison.

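### Five imputations leave avoidable Monte Carlo error in the model-based sensitivity analysis of the primary endpoint; it changes the reading only when p is near 0.05

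*SAP*

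**What the plan says.** SAP 9.1.3 plans three ways of filling in missing daily pain scores from Day 1 to Day 28: model-based multiple imputation (Method 1), LOCF (Method 2) and BOCF (Method 3). For Method 1 the text reads "Individual missing scores will imputed 5 times", gives one seed, and says that the results "will be summarized into 5 individual ANCOVA models", which are then pooled in PROC MIANALYZE. The code has the same number and seed: "PROC MI DATA=ADAM NIMPUTE=5 SEED=8743216514 MINIMUM=0 MAXIMUM=10".

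The SAP attaches a literature reference to the number five. It states no expected missing-data rate, no tolerance for Monte Carlo error and no rule for raising the number.

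The pooled output is an estimate, standard error, 95% confidence interval and p-value. SAP 5.6 says "All p-values will be tested using alpha at the 0.05 level, two-tailed", and SAP 5.3.5 says "P-values will be reported out and rounded off to 4 numbers after the decimal point".

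**The concern.** Multiple imputation draws random values, so its pooled result varies from seed to seed. The variation shrinks as the number of imputations grows, and five is few. If the noise is not small beside the standard error, the reported p-value is partly an accident of the seed, yet it is given to four decimals and read against 0.05.

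At stake is how well this one analysis does its job. The primary ANCOVA uses observed weekly means without imputation (SAP 9.1 and 9.1.2), so the sensitivity analyses carry the missing-data question. LOCF and BOCF fill each gap with a single value. Of the three imputation methods, only Method 1 reflects imputation uncertainty, and it should not add noise that could be removed at no cost.

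**Working it through.** **Inputs from the documents.** Number of imputations m = 5 (SAP 9.1.3, text and code). Two-sided alpha 0.05 (SAP 5.6). 75 subjects per arm, difference 1.05, SD 2.25 (SAP 4.4).

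**Inputs assumed.** Neither document gives a dropout or missing-data rate. I take missing information (FMI) of 2%, 5% and 10%, and show 20% as an upper case.

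**Step 1: reproduce the plan's own figure.** SAP 4.4 states "A sample size of 75 subjects per group will provide approximately 80% power" "when the mean difference from placebo is 1.05 and the standard deviation is 2.25".

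- SE of a difference = 2.25 x sqrt(2/75) = 0.367 NRS points.
- 1.05 / 0.367 = 2.858.
- Power = 0.815 (normal approximation) or 0.810 (noncentral t, 148 df).

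The stated figure is reproduced.

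**Step 2: Monte Carlo error.** As a share of the SE it is sqrt(FMI/m). For a result whose p-value with unlimited imputations (the limiting p) is 0.05, z = 1.96, and 95% of seeds give z within 1.96 +/- 1.96 x sqrt(FMI/m). The last column multiplies the error by 0.367.

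| FMI | Error, m = 5 (share of SE) | z range | p range | Error (NRS points) |
|---|---|---|---|---|
| 2% | sqrt(0.02/5) = 0.06 | 1.836 to 2.084 | 0.037-0.066 | 0.02 |
| 5% | sqrt(0.05/5) = 0.10 | 1.764 to 2.156 | 0.031-0.078 | 0.04 |
| 10% | sqrt(0.10/5) = 0.14 | 1.683 to 2.237 | 0.025-0.092 | 0.05 |
| 20% (upper case) | sqrt(0.20/5) = 0.20 | 1.568 to 2.352 | 0.019-0.117 | 0.07 |

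**Step 3: which FMI is plausible.** Missing information is not the same as dropout. Earlier daily scores inform the imputation, and a Week 4 mean with at least four observed days is not recalculated. A simulation of Method 1 used 4 x 75 subjects, 28 daily change scores, a Week 4 SD of 2.25, dropout on Days 1 to 24, ANCOVA and Rubin pooling. It omitted the 0 to 10 bounds in the code. Dropout rates and day-to-day correlations (high and moderate) are assumptions.

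| Dropout | FMI | p range at m = 5, limiting p 0.05 (high; moderate correlation) | Seeds giving p > 0.05, limiting p 0.04 | Same, limiting p 0.03 |
|---|---|---|---|---|
| 5% | 1-2% | 0.040-0.064; 0.037-0.069 | 5-10% | 0-0.3% |
| 10% | 3-5% | 0.035-0.073; 0.030-0.084 | 14-24% | 1-5% |
| 15% | 4-9% | 0.032-0.080; 0.026-0.100 | 19-32% | 3-12% |
| 20% | 6-12% | 0.029-0.086; 0.023-0.111 | 25-36% | 5-16% |

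At a limiting p of 0.01, at most 0.4% of seeds cross 0.05 in any scenario.

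**Step 4: more imputations.** In the same simulation, from the mildest scenario (5% dropout, high correlation) to the worst (20% dropout, moderate correlation), a limiting p of 0.05 ranges over:

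- m = 50: 0.047-0.054 to 0.040-0.063.
- m = 100: 0.048-0.052 to 0.043-0.058.

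At a limiting p of 0.04, the share of seeds giving p > 0.05 falls from 5-36% (m = 5) to 0-4% (m = 50) and 0-1.3% (m = 100).

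**The case against.** The other side has a good deal that stands.

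- **The seed is fixed in text and code.** A rerun gives the same answer, and the seed cannot be picked after unblinding. What remains is arbitrary noise in a reproducible number. A fixed seed does not bring that number closer to what the method would give with many imputations.
- **Method 1 is not the only principled check.** A reader might infer that a seed-dependent result leaves the primary analysis without a usable missing-data check. The documents do not support that. Protocol 12.5.1.2 names an MMRM as the sensitivity analysis, and SAP 5.3.5.3 and 9.2.2 plan it for the same pain score over Weeks 1 to 4 without imputation. It has no seed.
- **The size depends on an unstated rate.** It is tempting to lead with 20% missing information and a p range of 0.019-0.117. That FMI lies above every simulated scenario (1-12%), although the worst simulated range, 0.023-0.111, comes close. At 5% dropout the effect is modest, and with almost complete data it would be negligible.
- **The noise is small on the pain scale.** Even at 20% missing information it is about 0.07 NRS points against a planned difference of 1.05. The estimate and confidence interval are reported too, and no decision rule hangs on this p-value.
- **The number five is referenced.** The source cannot be checked here, and the SAP adds no argument for this trial.

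**Conclusion.** The point holds as a minor, cost-free improvement. With five imputations, Method 1 carries Monte Carlo error of 0.06 to 0.14 of the SE at 2-10% missing information, enough to move a p-value near 0.05 in its second decimal. These sizes rest on assumed missing information, since the documents state no rate; 2-10% roughly matches the 1-12% simulated for 5-20% dropout.

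The significance reading is at risk only near the threshold. At a limiting p of 0.04 between 5% and 36% of seeds would cross it; at 0.01 almost none would. It would be wrong to conclude that the result is irreproducible, open to manipulation or unable to inform the primary analysis. The primary ANCOVA, LOCF, BOCF and MMRM are untouched.

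**What to change.** Raise the number of imputations to 100 and keep a prespecified seed. Three places in SAP 9.1.3 need the same number: the count of imputations in the Method 1 text, the count of ANCOVA models to be pooled, and the NIMPUTE option in the code. One hundred is not a uniquely right figure; 50 already removes most of the noise, and a stated limit on Monte Carlo error would also serve.

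The cost is computing time only. No endpoint, population, model or trial procedure changes. SAP 4.6 has the plan signed off before database lock and unblinding, so the edit belongs before that sign-off.

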4.2 Subject Randomization

At the Baseline visit, average daily pain scores and diary compliance will be transferred into the interactive response technology system, which will be used to assess the following criteria for randomization^[4]:

Eligible subjects will be randomized to receive either NYX-2925 10 mg daily, NYX-2925 50 mg daily, NYX-2925 200 mg daily, or placebo for 4 weeks in a 1:1:1:1 allocation. The randomization will be stratified by study site.

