5.3.5.2 Analysis of Covariance Model

Using the change from baseline as a dependent variable, an analysis of covariance (ANCOVA) model with treatment (200 mg of NYX-2925, 50 mg of NYX-2925, 10 mg of NYX-2925, and Placebo) as the main effect and the baseline value as a covariate will be used to compare treatment groups at an individual analysis visit^[4]. The comparison of the NYX-2925 versus placebo will be assessed by forming the least squares means estimate of each particular NYX-2925 treatment groups stated in Section 5.2 and comparing them to the placebo group. The Kenward-Roger approximation will be used to estimate denominator degrees of freedom. Here is the SAS® code:

PROC MIXED DATA=ADAM ORDER=DATA METHOD=REML;

CLASS TRTP;

MODEL CHG = BASE TRTP / DDFM=KENWARDROGER;

LSMEANS TRTP / DIFF CL ALPHA=0.05;

/* -1 = Placebo; 0 = 10 mg of NYX-2925; 0.5 = 200 mg and 50 mg of NYX-2925 */

LSMESTIMATE "200 mg and 50 mg of NYX-2925 versus Placebo" TRTP 0 0.5 0.5 -1 / CL;

RUN:

The following ANCOVA model statistics for each treatment group will be presented in an analysis table:

- n =the number of records for that treatment or pooled treatment group
- Least Squares Mean for the treatment groups
- Standard Error for the treatment groups
- Least Squares Mean Difference for the NYX-2925 treatment groups versus Placebo
- Standard Error Difference for the treatment groups versus Placebo
- 95% Confidence Interval for the Difference for the treatment groups versus Placebo
- P-value for the Difference for the treatment groups versus Placebo

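### SAP 9.1.3 Method 1 puts the four-level treatment arm into a multivariate-normal imputation that cannot represent a category, so this sensitivity analysis cannot be carried out as written

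*SAP*

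**What the plan says.** SAP 9.1.3 plans three imputations of missing daily average-pain scores as sensitivity analyses of the primary endpoint: a model-based one (Method 1), last observation carried forward, and baseline observation carried forward. The Method 1 text reads: "The Markov chain Monte Carlo method will be used to compute full imputations using the following variables: planned treatment arm and scores at Study Day", the range being Days 1 through 28. The baseline score is not in that list.

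The printed code opens with "PROC MI DATA=ADAM NIMPUTE=5 SEED=8743216514 MINIMUM=0 MAXIMUM=10". It then names the arm variable TRTP in a CLASS statement, calls "MCMC INITIAL = EM" and lists "VAR TRTP BASE CHG1 -- CHG28". The code therefore uses arm as a category, the baseline score, and daily changes rather than daily scores. It creates no arm indicators and does not impute separately by arm.

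There are four arms: 10, 50 or 200 mg "or placebo for 4 weeks in a 1:1:1:1 allocation" (SAP 4.2). The ANCOVA run on each completed dataset is "MODEL CHG = BASE TRTP / DDFM=KENWARDROGER", with arm again a class variable. This matches SAP 5.3.5.2, where treatment is listed as four groups and enters "as the main effect and the baseline value as a covariate will be used to compare treatment groups".

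Imputed days count only where a weekly mean is otherwise unavailable: "the post-baseline analysis visits will be recalculated if they could not be calculated before". Under SAP 9.1 that means fewer than four observed daily scores in the week.

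**The concern.** MCMC imputation of this kind treats every listed variable as numeric and jointly normal. An unordered four-level arm has no place in that distribution unless it is recoded first, and the SAP gives no recoding. The method named in the text and the class variable in the code therefore do not fit together. The analysis that follows compares four separate arms, so the imputation model needs at least that much information about arm.

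The stake is what a repair might do. If arm were dropped, missing Week 4 values would be pulled toward a trajectory common to all arms, which dilutes dose effects. If arm were entered as one number, the imputed means would lie on a straight line across placebo, 10, 50 and 200 mg, although the ANCOVA makes no such assumption.

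The primary ANCOVA uses observed weekly means only, so a subject without a Week 4 mean contributes nothing to it. Method 1 is the one planned imputation for those subjects that is not a carry-forward rule.

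**Working it through.** **The plan's own figure.** SAP 4.4 gives a difference of 1.05, SD 2.25, 75 per arm and two-sided 0.05. SE of a difference = 2.25 × √(2/75) = 0.367. Power by normal approximation = Φ(1.05/0.367 − 1.96) = 81.5%; by noncentral t it is 81.0%. The stated 80% is reproduced and not in dispute. The SE serves below as a yardstick.

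**What a single number does to arm, by hand.** Assume an effect averaging −0.95 over Week 4, dropout after Day 7 and change SD of about 1.8. In a simulation of 40,000 per arm on these terms, omitting arm still leaves an imputed difference of −0.25, because the subject's observed days carry some arm information. The part left for the arm term is −0.95 + 0.25 = −0.70. With four equal arms coded 1 (placebo) to 4 (200 mg), the least-squares slope is Σ(x − 2.5)y / 5.
- Only 50 mg active: slope = 0.5 × (−0.70)/5 = −0.07. Imputed difference at 50 mg = −0.25 + 2 × (−0.07) = −0.39; at 200 mg, 3 × (−0.07) = −0.21 where the truth is 0. The simulation gave −0.40 and −0.22.
- 50 and 200 mg both active: slope = (0.5 + 1.5) × (−0.70)/5 = −0.28, so 10 mg receives −0.28 where the truth is 0. The simulation gave −0.28.

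At 10% of each arm imputed, the arm difference moves by (0.95 − 0.25) × 0.10 = 0.07 with arm omitted. With the number it moves by (0.95 − 0.40) × 0.10 = 0.055 at the active dose and 0.22 × 0.10 = 0.022 at the inactive one.

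**Effect on the Week 4 ANCOVA.** A second simulation (40,000 per arm, monotone dropout, normal-theory imputation, baseline in the model, no bounds) gave these estimates where the true difference is −1.05:

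| Arm entered as | True differences at 10, 50, 200 mg | 10% dropout | 20% | 30% |
|---|---|---|---|---|
| three indicators | 0, −1.05, −0.20 | −1.04 | −1.05 | −1.04 |
| one linear number | 0, −1.05, −0.20 | −0.99 | −0.95 | −0.92 |
| omitted | −0.35, −0.70, −1.05 | −0.96 | −0.91 | −0.83 |

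Arithmetic check: estimate ≈ (1 − p) × (−1.05) + p × (imputed difference).
- Linear number, p = 0.2: imputed means are −1.82 (50 mg) and −1.24 (placebo), a difference of −0.58. Then 0.8 × (−1.05) + 0.2 × (−0.58) = −0.96.
- Arm omitted, p = 0.2: −1.88 + 1.59 = −0.29. Then −0.84 − 0.06 = −0.90.

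Both agree with the table to within 0.01. Runs with arm entered correctly ranged from −1.01 to −1.08, so simulation scatter is up to 0.04.

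**Equal dose steps.** With true differences −0.35, −0.70, −1.05 and a linear number at 30% dropout, the imputed means were −1.21, −1.56, −1.90, −2.22 against true −1.21, −1.57, −1.90, −2.22: no bias.

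**Baseline left out, arm as indicators.** Estimates stayed within about 0.05 of the truth and imputed means still followed the arm.

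**Bounds in the same code.** With indicators and baseline but the 0 to 10 limits applied to changes, imputed Week 4 changes averaged about +1.0 to +1.3 in every arm (truth −1.2 to −2.3). A true −1.05 shrank to −0.96, −0.90 and −0.76 at 10%, 20% and 30% dropout.

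**The case against.** The strongest reply is that no bias follows from the plan as printed. Either the step fails, and then there are no imputed values, or someone recodes arm. The text names arm as an imputation variable, so dropping it would depart from the plan, and indicators are an obvious repair. That stands: the shrinkage above belongs to two possible repairs, not to the SAP. A reader might infer that imputed pain will not follow the subject's own arm, or that dropping arm or numbering it are the only ways to run MCMC. Neither is supported, since three indicators or separate imputation by arm also work.

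A reader might also state flatly that the code will not run. The documents do not say how the software behaves, so that should be tested. The mismatch between a joint normal model and a category does not depend on the answer.

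Nor is baseline missing from the imputation model: the code has it, and only the text lacks it. Its omission would not stop imputations following the arm.

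Importance is limited too. SAP 5.3.5.3 and 9.2.2 plan an MMRM of the same score over Weeks 1 to 4, with four treatment groups, their interaction with visit, and baseline. It uses the dropouts' available earlier weekly means without this fault, and protocol 12.5.1.2 names this type of model as the sensitivity analysis. No decision rule hangs on Method 1. SAP 4.6 lets analyses be produced after unblinding but does not say when code is tested, so a claim that the repair would be chosen with treatment codes known is only inference.

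**Conclusion.** The point holds in limited form. Method 1 specifies a model that cannot take arm as the four-level category that its own text, code and ANCOVA require. If the repair were to omit arm or number it, a true −1.05 would lose about 0.06 to 0.09 at 10% dropout (0.16 to 0.25 of the 0.367 standard error) and 0.10 to 0.14 at 20% (0.27 to 0.38). The other simulation gives 0.02 to 0.07 at 10% imputed. For the linear number at 10% the loss is not far above simulation scatter, and it is nil if dose steps are equal.

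Dropout share and timing, correlations and dose-response shapes are all assumptions, because the SAP gives none. The omission of baseline from the text is a separate mismatch of minor effect. A reader might take any of this as a threat to the primary result. It is not: the observed-data ANCOVA and the MMRM do not use this step.

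**What to change.** In the imputation step, remove the CLASS statement for arm and replace TRTP in the variable list by three 0/1 indicators for 10, 50 and 200 mg. Alternatively, use FCS regression with arm as a class variable. Keep arm as a four-level class variable in the ANCOVA.

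Add the baseline mean score to the imputation variables named in the text, and state whether scores or changes are imputed, so that text and code agree. Correct the 0 to 10 bounds at the same time, since those limits suit scores and not changes; the arm fix alone does not make Method 1 valid.

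Test the revised code on blinded or dummy data before database lock. The cost is a sentence or two and a few code lines in the SAP, with no new data and no further subjects.

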5.1.5 Change from Baseline

If both post-baseline and baseline values are present/imputed, then change from baseline is defined as each post-baseline value – baseline value. Otherwise the change from baseline will not be reported.

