9.1 Primary Efficacy Data

The primary efficacy data for this study is the NRS score assessing average pain intensity in the past 24 hours. Daily collected pain scores are based on an 11-point numerical rating scale/Likert scale ranging from 0 to 10. Where 0 represents no pain and 10 is the worst pain imaginable^[2].

The mean NRS score assessing average pain intensity in the past 24 hours will be calculated for the analysis visits described in Section 5.4.2^[4]:

- Baseline (average of Study Days -7 to -1)
- Week 1 (average of Study Days 1 to 7)
- Week 2 (average of Study Days 8 to 14)
- Week 3 (average of Study Days 15 to 21)
- Week 4 (average of Study Days 22 to 28)

The mean baseline visit will be calculated if at least 6 of the study days have a reported pain score. This is a requirement in order to be eligible for being randomized to a study drug treatment arm. There will need to at least 4 daily pain scores collected within a post-baseline analysis visit in order to calculate the mean pain score for that visit.

Each mean analysis visit score will take on values ranging from 0 to 10 and will be rounded off by one number after the decimal point. Data prior to Study Day -7 or after Study Day 28 will not be used in the mean calculated scores. No missing data imputations will be used for these observed means, but Section 9.1.3 will explain imputation methods used for sensitivity analyses.

The actual means, change from baseline, and percent change from baseline at each analysis visit will be summarized using descriptive statistics. The same descriptive statistics table will be additionally provided by each study site, age groups, gender, race, ethnicity, and subjects using or not using at least 1 concomitant analgesic medication at Baseline. All data collected and derived will be presented in subject listings.

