9.3.2 Responder Status Endpoints

Different efficacy responder statuses will be defined based on the following methods [4, 10]:

- Responder at $\geq 30\%$ Pain Reduction:
 - Subjects achieving ≥30% pain reduction on the mean NRS score assessing average pain intensity in the past 24 hours from baseline to Week 4 analysis visit and the subjects must complete the study. Subjects who do not have an analysis visit Week 4 mean NRS score assessing average pain intensity in the past 24 hours will be set to a non-responder.

- Responder at ≥50% Pain Reduction:
 - Subjects achieving ≥50% pain reduction on the mean NRS score assessing average pain intensity in the past 24 hours from baseline to Week 4 analysis visit and the subjects must complete the study. Subjects who do not have an analysis visit Week 4 mean NRS score assessing average pain intensity in the past 24 hours will be set to a non-responder.
- Responder at ≥30% Pain Reduction and Week 4 PGI-C Improved Score:
 - Subjects achieving ≥30% pain reduction on the mean NRS score assessing average pain intensity in the past 24 hours from baseline to Week 4 analysis visit and the subjects must complete the study. Subjects who do not have an analysis visit Week 4 mean NRS score assessing average pain intensity in the past 24 hours will be set to a non-responder.
 - o In addition, to be classified as "responders" subjects must have an analysis visit Week 4 PGI-C score of 1 (Very Much Improved) or 2 (Much Improved). Otherwise, those subjects will be set to non-responders.

The percent change from baseline that is \leq -30.0% is equivalent to \geq 30% pain reduction. Subjects with a calculated mean NRS score assessing average pain intensity in the past 24 hours at analysis visit Week 4 will be provided in a figure based on their percent change from baseline values. The horizontal axis displays a range of percentage-reductions from baseline at Week 4 in the mean NRS score assessing average pain intensity in the past 24 hours and the vertical axis displays the percentage of subjects achieving each of those levels of improvement. The horizontal axis will range from 0% to 100% in percentage-reductions and will not plot subjects with percentages below 0% (i.e. subjects that showed worse pain at Week 4 and the percentage change from baseline \geq 0%).

Frequency distributions, odds ratio, and relative risk analyses described in Section 5.3.5.5 will be used to summarize the responder status endpoints.

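### The SAP text for Method 1 imputes daily pain scores, but its code imputes changes from baseline limited to 0–10, so no imputed day can show improvement.

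*SAP*

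**What the plan says.** **Text.** In SAP 9.1.3, Method 1 imputes individual missing daily scores five times from "planned treatment arm and scores at Study Day 1 through Day 28". SAP 9.1 gives the scale: "Daily collected pain scores are based on an 11-point numerical rating scale/Likert scale ranging from 0 to 10". Imputed days have a restricted use: "the post-baseline analysis visits will be recalculated if they could not be calculated before". A week with at least 4 observed scores keeps its observed mean. Five ANCOVAs are then combined to give LS means, differences from placebo, confidence intervals and p-values, with counts for single and pooled treatment groups.

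**Code.** The imputation step reads "PROC MI DATA=ADAM NIMPUTE=5 SEED=8743216514 MINIMUM=0 MAXIMUM=10", and its variable list is "VAR TRTP BASE CHG1 -- CHG28". The averaging step runs "BY _IMPUTATION_ AVISIT". PROC MIXED then models CHG on BASE and TRTP, and PROC MIANALYZE lists only the intercept and TRTP as effects.

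**Sign of change.** SAP 5.1.5 states that "change from baseline is defined as each post-baseline value" minus the baseline value. SAP 9.3.2 treats a percent change of -30.0% or lower as a pain reduction of at least 30%. It leaves values of 0% or above off its responder figure, describing them as "subjects that showed worse pain at Week 4 and the percentage change from baseline".

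**The concern.** Limits of 0 and 10 suit the raw score but are applied to the change. A change of 0 or more means no improvement, so an imputed day can never show benefit, whatever the subject's observed days or the treatment arm would predict.

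The primary ANCOVA uses observed Week 4 means and so omits subjects with fewer than 4 Week 4 scores. Method 1 is the only multiple-imputation analysis set against that omission. As coded, it does not draw from what the model predicts for those subjects. It is harsher than BOCF, which assigns exactly no change, yet its table is labelled model-based. A reader would take it as a check under data missing at random, which it would not be. The error can shrink or exaggerate the treatment difference, depending on which arm has more missing data.

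Two later steps also disagree with the text. Averaging by imputation and visit alone gives one mean for all subjects and drops the TRTP and BASE that PROC MIXED needs. The combining step does not collect the LS means or the pooled 200 mg and 50 mg contrast.

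**Working it through.** **1. Planning inputs (SAP 4.4).** Difference 1.05, SD 2.25, 75 per group, two-sided alpha 0.05. The noncentrality is 1.05 / (2.25 × √(2/75)) = 2.86, which gives power of 81.0% from the noncentral t. This reproduces the SAP's figure of approximately 80%, so the two inputs are used below.

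**2. What the limits permit.** For a baseline mean b, a score of 0 to 10 means a change of -b to 10 - b. The code permits a change of 0 to 10, that is, an implied score of b to b + 10.

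| Baseline b | Possible change | Score implied by the code |
|---|---|---|
| 4 | -4 to 6 | 4 to 14 |
| 7 | -7 to 3 | 7 to 17 |

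Both ends are wrong: improvement is impossible, and scores above 10 are allowed.

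**3. Share of plausible values excluded.** The documents give no placebo change, so a Week 4 mean change m of -1 to -2 is assumed, with active 1.05 lower and a normal distribution with SD 2.25. The share below 0 is Φ(-m/2.25).

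- Placebo: Φ(1/2.25) = 67% to Φ(2/2.25) = 81%.
- Active: Φ(2.05/2.25) = 82% to Φ(3.05/2.25) = 91%.

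**4. Mean imputed change.** With a = -m/2.25, the mean of a normal distribution cut at 0 is m + 2.25 × φ(a) / (1 - Φ(a)); the cut at 10 has a negligible effect. For m = -1 this is -1 + 2.25 × 0.3614 / 0.3284 = +1.48.

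| Assumed placebo / active change | Imputed mean, placebo | Imputed mean, active |
|---|---|---|
| -1 / -2.05 | +1.48 | +1.22 |
| -1.5 / -2.55 | +1.35 | +1.12 |
| -2 / -3.05 | +1.23 | +1.04 |

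**5. Effect on the treatment difference.** Each arm's mean is (1 - f) × true mean + f × imputed mean, where f is the assumed fraction without an observed Week 4 mean. For m = -1 with 10% missing on placebo and 20% on active:

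- Active: 0.80 × (-2.05) + 0.20 × 1.22 = -1.396.
- Placebo: 0.90 × (-1) + 0.10 × 1.48 = -0.752.
- Difference: -0.64, against a true -1.05.

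The feasible-limits column repeats the calculation with the change limited to -6.5 to 3.5. These are the limits that 0–10 scores imply at an assumed baseline of 6.5.

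| Missing, placebo / active | As coded | With feasible limits |
|---|---|---|
| 5% / 5% | -1.01 | -1.04 |
| 15% / 15% | -0.92 to -0.93 | -1.02 to -1.03 |
| 10% / 20% | -0.56 to -0.64 | -1.00 to -1.03 |
| 20% / 10% | -1.22 to -1.29 | -1.03 to -1.04 |

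**6. Conditioning on a subject's own data.** Steps 3 to 5 ignore the days already observed. A second calculation used a random-intercept daily model scaled to a weekly-mean SD of 2.25, with dropout at random after Day 14. Each Week 4 day was drawn given Days 1–14 and limited to 0–10, with day-to-day correlation assumed at 0.5, 0.7 and 0.85. Imputed means were +0.56 to +1.58 on placebo and +0.38 to +1.29 on active. In the row order of the table above, the differences were -1.01, -0.92 to -0.94, -0.55 to -0.71 and -1.15 to -1.30. The pattern is the same.

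**The case against.** The strongest reply is that this is a drafting error in abridged code. As printed, the code cannot reach the ANCOVA. It imputes one variable per day and then averages a single CHG variable without any restructuring, and the averages do not carry TRTP or BASE. A programmer must depart from it, and the text already describes the right imputation. That is fair as a description, but rebuilding the later steps would not expose the wrong limits, and the SAP would still hold two conflicting specifications.

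The reply on weight largely stands. The SAP calls Method 1 model-based and never claims that it is a missing-at-random check. The protocol's named sensitivity analysis is the MMRM, which the SAP keeps without imputation. Table 14.2.1.2.2 is not marked for topline. The large shifts need an assumed 10-point gap in missingness that nothing in the documents supports for a 4-week trial.

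Correct score limits also truncate, so the fairer comparator is the feasible-limits column. Against it, the error is about 0.03 at 5% missing in both arms and 0.10 at 15%, rather than 0.04 and 0.12–0.13 against -1.05. The unequal-missingness rows barely move.

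On the combining step, placebo appears to be the last level of TRTP, so the TRTP effects may already be the dose-versus-placebo differences. The LS means and the pooled contrast would still not be combined.

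**Conclusion.** The point holds. Text and code impute different quantities, and as coded no imputed day can show improvement. This follows from the SAP's own definitions and needs no numerical assumption beyond reading the single pair of limits as applying to every imputed change variable.

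The size does rest on assumptions about missingness, placebo response and distribution. With low, balanced missingness the error is small: about 0.03 at 5% and 0.10 at 15%. With a 10-point imbalance, the planned effect of 1.05 could appear as 0.56–0.64 or as 1.22–1.29. Only subject-weeks with fewer than 4 observed scores are touched, and only in the Method 1 table. It should be fixed, but it does not threaten the primary result.

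**What to change.** Make the Method 1 code follow the text:

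- Impute the raw daily scores for Days 1–28 with limits 0 and 10, then derive changes from baseline.
- Average by imputation, subject and visit, carrying TRTP and BASE. Use imputed days only for weeks that could not be calculated from observed scores.
- Pass the LS means, the three dose-versus-placebo differences and the pooled 200 mg and 50 mg contrast to PROC MIANALYZE.

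This is a few lines of SAP code. It should be settled before database lock, because choosing between text and code after unblinding would be a post hoc decision. No new data are needed and no other analysis changes.
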